**Understanding Cytokine Storm Syndrome through Multi-Omic Systems Biology.** Infection with SARS-CoV-2 and other viruses may lead to significant alterations in the host transcriptome and modulated immune response(80, 81). In PBMCs of COVID-19 patients, more than 1,000 genes were reported to be differentially expressed compared to controls. Some of these genes are directly involved in immunity, such as humoral responses, lymphocyte-mediated immunity and complement activation. Thus, studying transcriptomic changes provides a high resolution understanding of SARS-CoV-2-induced immune activity in PMBCs. Up- and downregulated PBMC genes are also involved in other biological processes, such as protein translation(64). *Immunophenotyping* generates systemic and tissue specific immune profiles. Patients with severe COVID-19 often present with profound lymphopenia, develop neutrophilia, and high hemoglobin levels(72, 82, 83). Immune cell ratios and activation, as well as inflammatory mediators, are associated with disease state and prognosis(46, 56, 82, 84-86). Immunophenotyping analysis demonstrated decreased levels of lymphocytes, including NK, T, B, and Treg cells, as well as monocytes(55, 68, 72). A heterogeneous interferon-stimulated gene signature, downregulation of HLA class II, and a novel B cell-derived granulocyte population have also been identified(87). A recent multi-omic analysis by RNA-seq and high-resolution mass spectrometry on 128 blood samples from COVID-19-positive and -negative patients with diverse disease severities mapped 219 molecular features with high significance to COVID-19 status and severity involved in complement activation, dysregulated lipid transport, and neutrophil activation (88). While presenting the most comprehensive evidence of predictive potential of COVID-19-related outcomes based on multi-omic analysis, the authors conclude that limitations include the single-center restricted demographics of the population not representing “replicate factors related to, among others, geography or population socioeconomic status” and the fact that the “study was not powered to demonstrate the association of omic data with survival, which is the most impactful patient-centered outcome measure” (88). *We intend to address both of these limitations in our study.*

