**Data Collection.** The data collection method is simple, cost-effective, and minimally invasive, requiring *only one research blood draw at enrollment*, abstraction of clinical parameters from the electronic medical record, and a brief interview at enrollment, at discharge, and at one year. **Clinical Data.** Demographics, laboratory values, organ function parameters, frailty parameters, comorbidities, disability data as well as COVID-19 treatment data will be collected. **Table 1** summarizes the *routine clinical laboratory values* to be collected. Validated *organ function scores*, such as SOFA score, MELD-XI score, the Seattle Heart Failure Model will be calculated(105-107). *Comorbidities* will be assessed using Charlson and Elixhauser scoring systems(108, 109). Risk of alcohol use disorders will be assessed with AUDIT-C (110). *National Health Service Frailty Scale* scores will be assessed(111). All clinical data will be collected at baseline, at discharge and at one year after COVID-19 enrollment, abstracted into REDCap, and later analyzed using R (Vienna, AU). All patients will be interviewed in person (if not available, then by televisit) at discharge and one year after enrollment. *The National Death Index* will be searched for subjects who are uncontactable(112). **Blood Collection and Processing.** Research blood will be collected within 72h of admission and COVID-19 diagnosis confirmation and processed within 2h of sampling, into one 8 ml CPT tube (BD Biosciences) for PBMC transcriptomic analysis and cfDNA analysis and one 8 ml ACD tube (BD Biosciences) for immunophenotyping and cytokine concentration analysis. Each study site will isolate plasma and PBMC using standard procedures, aliquot these samples in duplicates and store samples at -80°C. Samples will be shipped in batches to UCLA on dry ice by express delivery. **cfDNA Sequencing.** The Illumina NovaSeq platform will be used to sequence paired-end reads of cfDNA for 2x150 bp with 1% Phix control using S4 flow cell. For cfDNA concentration quantification, we will use Invitrogen Qubit™ dsDNA HS Assay Kit and Invitrogen Qubit 2.0 Fluorometer. Then, cfDNA sequencing will be done on an Illumina HiSeq 3000. **RNA Sequencing.** Total RNA will be isolated from PBMC(25)(90). Purified RNA quality will be verified on an Agilent 2100 Bioanalyzer. RNA concentrations will be determined using a NanoDrop ND-1000 spectrophotometer. The mRNA library will be prepared with Illumina TruSeq RNA kit. The cDNA libraries will be quantitated using Qubit. Total mRNA will be amplified and sequenced on the whole-genome Illumina HiSeq 3000. **Flow Cytometry.** Immunophenotyping of PBMCs will be performed with 12-color monoclonal antibody panels to identify the subpopulations listed in **Table 2**. Cell fluorescence will be acquired on an LSR Fortessa™ cell analyzer, using standard acquisition templates. **Cytokine Quantification.** We will quantify plasma cytokine levels using a 38 multiplex Luminex array. Fluorescence intensity is acquired using a Luminex 200 instrument and xPONENT software.

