
**Sample Size Requirements and Power Calculations.** Current available literature suggests that at least 20% of the symptomatic COVID-19 infected population may develop frailty, organ dysfunction or death within one year(46, 47, 52, 56, 57, 61, 62, 113-116). Based on these assumptions, we will perform power calculations on the following numbers (250 civilians, 250 Veterans) (**Figure 2**): Aim 1.1 single-omic identification (n=100, 80 endpoint negative/20 endpoint positive) and confirmation (n=200, 160 endpoint negative/40 endpoint positive) of candidate genomic, transcriptomic, proteomic and clinical parameters that correlate with outcomes; Aim 1.2 multi-omics correlation analysis (n=300 from Aim 1.1, 240 endpoint negative/60 endpoint positive); Aim 1.3 WGCNA and pathway analysis (n=300 from Aim 1.1); Aim 2.1 training/testing of the predictive algorithm (n=300 from Aim 1.1); Aim 2.2 independent validation of predictive algorithm (independent n=200). Samples will be processed in 5 batches, approximately 120 samples per year within 5 years. Statistical analysis will begin after one-year outcomes of the first 100 patients have been collected. Patients will be stratified by outcomes, Veteran/civilian status, age, gender, ethnicity, comorbidities, frailty and other parameters that appear to be significant such as alcoholism.

**Timeline.** The timeline of the entire project is summarized in **Table 3**. We anticipate that: 1) recruitment of 600 COVID-19 patients will be begin 3 months after funding start, be completed within 42 months, 2) the 12-month follow-up period will be completed by month 57, and 3) the analysis will be completed by month 60.

Immune Cell Subsets	
Cell Population	Phenotype
T cells	CD3+CD4+ or CD3+CD8+
Naive	CCR7+CD45RA+
Effector Memory	CCR7-CD45RA-
Central Memory	CCR7+CD45RA-
TEMRA	CCR7-CD45RA+
Activated Effector	CD25++CD127hi
Regulatory	CD4+CD25++CD127lo
Antigen-experienced	KLRG1+
Limited capacity memory	CD38+
Chronically activated	CD57+
Activated suppressive	PD1+
Natural Killer Cells	CD3-CD56+
Cytotoxic	CD56dimCD16+
Cytokine producing	CD56brightCD16+
B Cells	CD19+
Transitional	CD38++CD24+
Mature Naive	CD27-IgD+
Memory	CD27+
Non-Switched memory	CD27+IgD-
Switched Memory	CD27-IgD+
Plasmablasts	CD27+CD38++
Regulatory	CD5+CD24+

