## SPECIFIC AIMS

**AIM 1: CORRELATE MULTIOMIC DATA WITH OUTCOMES. Hypothesis and Objectives.** We hypothesize that various clinical COVID-19 disease outcome phenotypes correlate with molecular data and clinical patterns and are associated with immunologic pathways. Our first objective is to identify and confirm mono-dimensional genomic, transcriptomic, proteomic and clinical parameters that correlate with outcomes (Aim 1.1). Outcomes are defined as new onset or worsening frailty, single organ dysfunction, multiorgan dysfunction, and death within one year (primary endpoint) and at time of discharge (secondary endpoint). Since genomics, transcriptomics and proteomics often have complementary roles, our second objective is to perform multi-omics correlation analysis (Aim 1.2). Our third objective is to perform Weighted Gene Co-Expression Network Analysis (WGCNA) and pathway analysis to understand the role of the genes involved in the inflammatory response during SARS-CoV-2 infection (Aim 1.3).

**Aim 1.1: Single-omic identification of candidate genomic, transcriptomic, proteomic and clinical parameters that correlate with outcomes. Objective.** Our objective is to identify single-omic parameters (genomic, transcriptomic, proteomic) and clinical data that correlate with COVID-19 outcomes. We will perform exploratory analyses on the first 100 samples and confirm these parameters on the following 200 samples (**Figure 2**). **Genomic Analysis.** Raw cfDNA sequences will be aligned to HG38 and cf-mtDNA to HG38\_MT\_only (Strand NGS 3.3.1). ComBat will be used for batch effect correction(164-166). We will calculate the number of cf-mtDNA fragments in each sample. **Transcriptomic Analysis.** Raw transcriptome data will be aligned (HG19) and normalized (DESeq), batch effect corrected by ComBat(164-166) and filtered by expression (20th to 100th percentile) (Strand NGS (Avadis)). Differentially expressed genes between positive and negative endpoint groups will be identified by non-parametric statistics (Mann-Whitney test with Benjamini-Hochberg correction). We will use a more relaxed criteria of FDR=0.1 and fold change of at least 2.0 to identify significant genes as previously described by our group(90, 167, 168). **Immunophenotyping Analysis.** We will identify COVID-19

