**Aim 1.3: WGCNA and pathway analysis. Objective.** The role of the genes involved in the inflammatory response during SARS-CoV-2 infection is unclear. To better understand co-expression of genes and their biological role in patients with symptomatic COVID-19, we will perform WGCNA and pathway analysis. To dissect the pro- and anti-inflammatory responses during SARS-CoV-2 infection with a non-supervised strategy, we will use WGCNA(170). WGCNA provides a non-supervised systematic method to identify co-expressed genes and pathways linked to the primary outcome. **Bioinformatics.** Normalized transcriptome data from the first 300 samples will be stratified by composite endpoint, batch effect corrected by ComBat and filtered by variance and entropy criteria to remove uninformative transcripts (**Figure 2**)(164-166, 169). This approach offers a powerful way to reduce dimensionality while enhancing biological interpretability. The co-expressed modules and their respective eigen-genes will be interpreted in their relationship to clinical and biological features. The clinical relevance of the modules will be inferred using a linear mixed effect model. The biological relevance of the modules will be deduced using gene ontology (GOSim(171, 172)) and pathway analysis (Strand NGS (Avadis)). **Interpretation of Results.** The results from WGCNA will offer a useful framework for relational and mechanistic reasoning. Our model will provide an integrative representation of leukocyte biology and related pathways during the COVID-19 inflammatory response. We anticipate that this strategy will enhance identification of candidate entities for the development of the prediction algorithm for adverse COVID-19 short- and long-term outcome events in Aim 2.

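### Gene and module results from bulk PBMC RNA cannot separate altered cell proportions from gene regulation when Aim 1 is read as pathway or mechanism

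*Protocol*

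**What the plan says.** In the protocol's Research Plan, under Data Collection, the RNA source is unsorted cells: "Total RNA will be isolated from PBMC". Aim 1.1 (Transcriptomic Analysis) lists alignment, DESeq normalisation, ComBat batch correction and an expression filter. Then "Differentially expressed genes between positive and negative endpoint groups will be identified by non-parametric statistics (Mann-Whitney test with Benjamini-Hochberg correction"), with thresholds "FDR=0.1 and fold change of at least 2.0 to identify significant genes". Discovery is on "n=100, 80 endpoint negative/20 endpoint positive" and confirmation on "n=200, 160 endpoint negative/40 endpoint positive".

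Aim 1.3 uses its own filter (variance and entropy) and then WGCNA. On interpretation it says: "The clinical relevance of the modules will be inferred using a linear mixed effect model". It presents the modules as a way to take apart pro- and anti-inflammatory responses and to support mechanistic reasoning. The Specific Aims make the biological role of the expressed genes a secondary goal.

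On cell mix, the Significance section says: "Patients with severe COVID-19 often present with profound lymphopenia". It links immune-cell ratios to disease state and prognosis, and also reports lower monocytes. Flow cytometry on PBMC from the same enrollment draw will count T, NK and B subsets; Table 2 lists no monocyte population. Table 1 includes the total lymphocyte count.

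**The concern.** In bulk RNA, the signal of a gene is its expression per cell averaged over the cell types present. If endpoint-positive patients have fewer lymphocytes relative to monocytes, monocyte genes rise and lymphocyte genes fall in the bulk measurement with no change inside any cell. The protocol's own background says this shift goes with severity, which is close to the contrast being tested.

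No listed processing step removes it. The Mann-Whitney test cannot take a covariate, and the Aim 1.3 model names none for composition. Co-expression analysis is especially exposed, because genes of one lineage move together whenever that lineage's share varies between patients.

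What is at stake is the mechanistic claim. A module that follows the monocyte share could be reported as an activated inflammatory programme.

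**Working it through.** **Plan's own figures.** The protocol gives no power, effect size or SD for the gene screen. Its group sizes reproduce: 0.20 × 100 = 20 and 0.20 × 200 = 40.

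**Inputs.** From the protocol: FDR 0.1, fold change at least 2.0, groups of 20 vs 80 and 40 vs 160, and 300 samples (60 vs 240) for Aim 1.3. Assumed, because the documents give no values: lymphocyte share of PBMC L = 0.7 to 0.9, the rest monocytes; equal RNA per cell; no change in expression per cell.

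**Fold change from cell mix alone.** Let the lymphocyte count in endpoint-positive patients be r times that in endpoint-negative patients, with monocytes unchanged. The new share is L2 = Lr / (Lr + 1 − L).

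- Monocyte-only gene, rise: (1 − L2)/(1 − L) = 1/(Lr + 1 − L).
- Lymphocyte-only gene, fall: L/L2 = (Lr + 1 − L)/r.

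With L = 0.8 and r = 0.5, Lr + 1 − L = 0.6. The monocyte-only gene rises 1/0.6 = 1.67-fold and the lymphocyte-only gene falls 0.6/0.5 = 1.20-fold. Both are below 2.0.

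**Fall in lymphocyte count needed for fold change 2.0.** Monocyte-only: r = (L − 0.5)/L. Lymphocyte-only: r = (1 − L)/(2 − L).

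| L | Monocyte-only genes | Lymphocyte-only genes |
|---|---|---|
| 0.7 | 71% | 77% |
| 0.8 | 62.5% | 83% |
| 0.9 | 56% | 91% |

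**Two limits.** A gene expressed 10 times higher in monocytes, but not only there, gives (0.6 + 10 × 0.4)/(0.8 + 10 × 0.2) = 4.6/2.8 = 1.64 at the 62.5% fall. If monocytes also fall by the factor r, L2 = L and every fold change is 1.

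**Passing both Aim 1.1 thresholds with no regulation.** Simulation with L = 0.8; log-SD 0.5 for counts and 0.5 for genes; 10,000 genes, of which 300 monocyte-only and 1,000 lymphocyte-only; 15 runs per setting, so percentages are approximate.

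| Lymphocyte fall | Monocyte-only genes passing, 20 vs 80 | 40 vs 160 |
|---|---|---|
| 40% | 2% | 0.5% |
| 50% | 24% | 4% |
| 62.5% | 43% | 40% |
| 70% | 82% | 79% |

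Lymphocyte-only genes passed in at most 5% up to a 70% fall. No gene unrelated to cell mix passed. At the larger falls the confirmation sample gives little protection, because the shift is real and repeats.

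**Aim 1.3, where no fold-change threshold applies.** Simulation of 60 vs 240 patients, 50 monocyte-only genes, no regulation, the same SDs, and the gene average standing in for the eigengene. With a 50% lymphocyte fall, the mean correlation between genes was 0.50, 0.57 and 0.63 for L = 0.7, 0.8 and 0.9. The gene average differed between endpoint groups at p < 0.001 in at least 99% of runs. A shift that is on average too small for the Aim 1.1 threshold can therefore still give an outcome-linked module.

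**The case against.** A reader might infer that lymphopenia alone will fill the Aim 1.1 list, or that Aim 1 and the algorithm are undermined. The documents do not support that.

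- **Aim 1.1 seeks correlates of outcome.** It names leukocyte subpopulations beside genes, so a transcript that marks cell mix is a legitimate result there and a legitimate predictor in Aim 2. There, LASSO models that include clinical factors are compared by AUC with a clinical-only model and then validated.
- **The fold-change-2 screen is confined to Aim 1.1.** It cannot be used to size the problem in Aim 1.3.
- **Striking examples need extreme inputs.** A lymphocyte share falling from 80% to 40% gives 2.0-fold and 3.0-fold changes. With monocytes unchanged it requires r = (0.4/0.6)/(0.8/0.2) = 0.167, an 83% lower count.
- **The background is mixed.** It also reports fewer monocytes, which would shrink the shift. It describes severe disease, whereas the contrast is the one-year endpoint, including frailty, among hospitalised patients.

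All four stand, and they limit the point to interpretation.

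It can also be said that the plan already handles composition. Aim 1.1 compares antigen-exposed subsets with the transcriptome, Aim 1.2 correlates subpopulations with outcome, and Aim 1.3 interprets modules against clinical and biological features. None of these is defined as adjusting a gene or module result. Covariates of the mixed model may be set in an analysis plan that is not at hand. That leaves the Aim 1.3 model open, but not the Aim 1.1 test, which the protocol fixes in a form that cannot adjust.

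Finally, altered composition is itself part of the immune response, so adjustment can remove real biology. That is a fair reason to report both results rather than the adjusted one alone.

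**Conclusion.** The point holds for mechanism and pathway statements. As written, the Aim 1.1 gene contrast and the Aim 1.3 module model cannot distinguish a changed cell mix from regulation per cell, although the protocol expects the mix to change with severity and measures most of it. It does not hold against Aim 1.1 as a screen or against Aim 2.

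The size is unknown from the documents. Under the stated assumptions, the Aim 1.1 threshold needs a large and uneven lymphocyte loss: 56% to 71% for monocyte-only genes across starting shares of 90% to 70%, and more for lymphocyte-only genes. A halved count stays below 2.0 on average. Aim 1.3 is more exposed, since a halved count is enough there. If all PBMC types fall in proportion, there is no artefact in either aim.

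**What to change.** For Aim 1.3, and for any pathway reading of the Aim 1.1 genes, fit the models with and without cell proportions. Use the linear and negative binomial models already planned in Aim 1.2, with the flow T, B and NK shares of PBMC as covariates. The monocyte share is then implied as the remainder and should not be entered as well; it is approximate, because Table 2 has no monocyte gate.

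Report both sets of results. Describe as gene regulation only associations that persist after adjustment, and report the others as possibly due to cell composition. Keep the unadjusted Aim 1.1 screen as the feed for the prediction model.

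The cost is extra analysis on data already planned, a few degrees of freedom per model, and probably fewer genes that can be called regulated. Sample size and error levels do not change.

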## **AIM 2: TRAIN AND VALIDATE ALGORITHM FOR OUTCOME PREDICTION**

**Hypothesis and Objectives.** We hypothesize that our algorithm will predict COVID-19 short- and long-term outcomes more accurately than clinical parameters alone. Our objectives are to train the algorithm in a mixed US-high risk COVID-19 population (Aim 2.1) and validate the predictive algorithm on an independent mixed US-high risk COVID-19 population (Aim 2.2).

**Aim 2.1: Train algorithm for outcome prediction. Objective.** Our objective is to train and test our algorithm in a mixed US COVID-19 population, which will improve prediction of adverse short- and long-term outcomes(92, 173). **Bioinformatics. Parameter Selection.** Model development will largely follow the modeling reported in the preliminary data section and will be constructed using significant entities identified in the marker screening phase (Aim 1). Since VA and civilian patients may have different co-morbidity and risk profiles, these models will also include a term for whether the patient is from the VA or civilian setting. This term, if significant, will allow flexibility in our models to make different predictions based upon known characteristic differences between VA and civilian patient populations. **Power calculations.** The first 300 samples (240 endpoint negative and 60 endpoint positive)

will be used for model building (**Figure 2**). The overall sample size will support the following: 1) This sample size will be sufficient to include approximately 10 clinical features based on conventional rules of thumb suggesting that we should have 10-15 subjects in the less frequent outcome category per variable in a logistic regression model; 2) This will allow us to estimate the AUC for the model with a precision of approximately 0.032 (based on the 95% confidence interval for the AUC and an overall AUC of at least 0.8); 3) Provide 80% power for detecting delta AUCs between pairs of models (see below) of 0.1 assuming that the models will have a correlation of 0.5 and AUCs of ~0.8. **Logistic regression modeling. Logistic regression modeling.** We will assess the algorithm by constructing three separate logistic regression models, one using clinical factors alone as our baseline model, one using clinical factors plus the significant omics markers from the screening phase (genomics, transcriptomics, and proteomics parameters), and one using clinical factors plus a simplified list of significant omics features (e.g. bedside, rapid test, easy to obtain). Each of the three models will have variable selection and coefficients estimated by the LASSO method and validation results and comparisons between the three models performance (AUC) will be validated in Aim 2.2. **Model building optimization by cross-validation.** Ten-fold cross-validation will be used to estimate model performance in terms of AUC. The AUCs will be compared between models with DeLong's test for paired AUCs. **Interpretation of Results.** We expect to derive a multi-omics algorithm that will predict outcomes of COVID-19 patients more accurately than clinical data alone.

**Aim 2.2: Independently validate predictive algorithm for outcome prediction. Objective.** Our objective is to validate the algorithm in an independent randomly selected mixed US COVID-19 population who were not used for algorithm development(173). **Bioinformatics.** We will validate the performance of the prototype test algorithm to predict the composite endpoints in an independent cohort of 200 patients (**Figure 2**). Rigorous testing of the analytical performance of the test will identify and quantify the technical variations of the test performed on the patient samples and will be done in a blinded fashion, without knowledge of the clinical status or treatment outcomes of the patients whose data was obtained. For model testing, the sample size of 200 (160 endpoint negative and 40 endpoint positive) will provide precision of +/- 0.066 for the testing AUC as well as an 80% power to detect differences in AUCs between models of 0.12, when comparing models based on clinical features alone and models combining clinical and molecular features. Finally, with this sample size we will be able to estimate the precision of the sensitivity and specificity (based on the width of the 95% confidence intervals) between 0.0545 to 0.11 depending on the observed values of those performance characteristics. *We plan to make the raw data and the algorithm publically available as a web-based free tool for further scientific development by the international scientific community.* **Interpretation of Results.** We expect that the algorithm will confirm the desired clinical test performance, i.e. increase accuracy of one-year primary endpoint (new onset or worsening frailty, organ dysfunction or death) prediction of at least AUC 0.12.

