**Patient Population.** We plan to complete 1-year follow-up in 500 patients from a large US-metropolitan area (LA-County) (n=250) and four national metropolitan VA centers (n=250). To account for a dropout rate of ~17%, we will recruit a total of 600 patients. LA-County is one of the largest metropolitan areas in the US. As per October 30, 2020, there were 290,278 laboratory confirmed cases, 24,670 hospitalized patients and 6,999 deaths(104). Since the first reported case of COVID-19 in the US, the four VA sites in Atlanta, Bronx, Houston and Los Angeles, have admitted 847 Veterans. While these sites vary in their COVID-19 experiences, combined they appear to be representative of the National VA population (**Table 1, re-submission Introduction**). These four sites belong to the SUPERNOVA consortium, which is a CDC-funded study ongoing for over 5 years that performs active surveillance for acute gastroenteritis and respiratory infection, including COVID-19 (28). The local site investigators are infectious disease physicians and have study staff trained in enrolling and following patients with infections. Study staff are well versed in identifying patients admitted with COVID-19, using a combination of admission log screening and TheraDoc (clinical surveillance software that integrates with the electronic medical record). Coordinators at the sites are experienced with abstraction of clinical data into REDCap and obtaining, processing, storing and shipping biological specimens. **Inclusion criteria.** Adult COVID-19 patients admitted to the hospital with any symptoms, including pneumonia, ARDS, sepsis, and septic shock(44) will be approached for consent (UCLA Informed Consent Form 20-000763, PI [name]). Since a majority of COVID-19-related deaths and hospitalizations are in male patients, we expect to enroll more men than women (9). **Exclusion criteria.** 1) Lack of consent by either patient or legally authorized representative, 2) <18 years old, 3) COVID-19 re-infection.

**Endpoint Definition.** Clinical composite endpoints will include new onset or worsening frailty, single organ dysfunction, multi-organ dysfunction, and death within one year (primary endpoint) and at time of discharge (secondary endpoint).

**Figure 1.** COVID-19 clinical decision making, study population and primary endpoint [modified after(96)].

**Figure 2.** Study design.

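### Under the protocol's own rule of 10 to 15 events per variable, the 60 events in the model-building set support 4 to 6 variables, including the VA/civilian term, not about 10 clinical features

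*Protocol*

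**What the plan says.** The protocol fixes the model-building set in two places. Aim 2.1 (Power calculations) reads "The first 300 samples (240 endpoint negative and 60 endpoint positive"), and continues that these "will be used for model building". The Research Plan (Sample Size Requirements and Power Calculations) agrees: "Aim 2.1 training/testing of the predictive algorithm (n=300 from Aim 1.1"), with a separate, independent 200 patients for validation in Aim 2.2.

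The event count rests on the assumption, in the same Research Plan section, that "at least 20% of the symptomatic COVID-19 infected population may develop frailty, organ dysfunction or death within one year".

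Aim 2.1 then introduces a list of sample-size properties with "The overall sample size will support the following". The first item is "This sample size will be sufficient to include approximately 10 clinical features based on conventional rules of thumb", and the rule is that "we should have 10-15 subjects in the less frequent outcome category per variable in a logistic regression model".

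Aim 2.1 also says that the models will carry a term for VA versus civilian setting. Three logistic models are planned: clinical factors alone, clinical factors plus the significant omics markers, and clinical factors plus a simplified omics list. Variable selection and coefficients in all three come from LASSO.

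**The concern.** The event count, the rule and the resulting number of features stand within a few lines of each other and do not agree. Dividing 60 by anything from 10 to 15 cannot give 10.

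The figure matters because it is the only guide in the protocol to how many clinical features the models may carry, and the pool is large. Table 1 alone lists 27 laboratory values, and Data Collection adds organ-function, comorbidity, alcohol-use and frailty scores. A team that relied on the stated capacity would work below the events-per-variable level that the protocol sets for itself. The clinical-only model is the baseline for the Aim 2 hypothesis, and the two omics models contain the same clinical factors, so the shortfall would enter every model being compared.

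**Working it through.** **Inputs, all from the protocol**
- Events in the model-building set: 60 of 300 (Aim 2.1, Power calculations). Check: 300 × 0.20 = 60.
- Rule: 10 to 15 subjects in the less frequent category per variable (Aim 2.1).
- Stated capacity: approximately 10 clinical features (Aim 2.1).
- Validation set: 200 patients, 40 of them endpoint positive (Aim 2.2).
- Completers: 500 (Patient Population). Recruited: 600 (same section).
- Additional term: VA/civilian, one parameter (Aim 2.1).

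**Formula.** Variables supported = events ÷ events per variable.

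**Attempt to reproduce the stated 10**

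| Patients counted | Events at 20% | At 10 per variable | At 15 per variable |
|---|---|---|---|
| Model building, 300 | 60 | 6 | 4 |
| Validation, 200 | 40 | 4 | 2.7 |
| All completers, 500 | 100 | 10 | 6.7 |
| All recruited, 600 | 120 | 12 | 8 |

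Only the 500 completers, at the lenient end of the rule, give exactly 10. Of those 100 events, 40 belong to the validation patients, who by the design of Aim 2.2 take no part in algorithm development. Removing them gives 100 − 40 = 60 events and a capacity of 4 to 6.

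**Allowing for the VA/civilian term.** It takes one place, which leaves 4 − 1 = 3 to 6 − 1 = 5 clinical features.

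**Events per variable at the stated capacity.** 60/10 = 6. With the VA/civilian term added to ten clinical features, 60/11 ≈ 5.5. Both are below 10.

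**What ten variables would need**
- Events: 10 × 10 = 100 to 10 × 15 = 150.
- Model-building patients at 20%: 100/0.20 = 500 to 150/0.20 = 750.
- Event rate if the set stays at 300: 100/300 = 33% to 150/300 = 50%.

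**Size of the overstatement.** 10/6 ≈ 1.7 to 10/4 = 2.5.

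**The case against.** Several points can be made for the plan.

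- **The wording points to the whole study.** The list of properties is introduced by reference to the overall sample size, and elsewhere the protocol says "We plan to complete 1-year follow-up in 500 patients". This probably explains where 10 came from. It does not rescue the figure, because the held-out 200 cannot support model fitting, and even 500 patients give only 6.7 variables at 15 per variable.
- **The 20% is a floor.** More events are possible, but Aim 2.1 fixes 60 for this calculation, and nothing in the protocol assumes the 33% to 50% that ten variables would require.
- **LASSO makes the rule less binding.** This has force: ten candidates under a penalty need not become ten fitted coefficients. But the protocol justifies its number by the rule and not by the penalty, so the stated justification still fails.
- **Ten is a capacity, not a commitment.** This is true. Aim 2.1 says development will largely follow the preliminary work, which used four clinical parameters. Four plus the VA/civilian term is five, within the corrected range. The error is in a stated property of the sample size, not in a pre-specified ten-variable model.

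A reader might also infer that the clinical model is bound to be overfitted, that it will lose AUC in validation, and that the omics gain will look larger than it is. The documents do not support that chain. All three models are penalised. The omics models contain the same clinical factors plus further candidates and are fitted on the same 60 events, so their own shortfall is at least as great. The comparison is then carried to independent patients, where the model with more candidates may lose as much or more. The difference in AUC could move either way.

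**Conclusion.** The figure is wrong as written. Under the protocol's own rule, the 60 expected events support 4 to 6 variables including the VA/civilian term, so the stated capacity of about 10 is 1.7 to 2.5 times too high. At ten features the models would have 6 events per variable against a stated minimum of 10.

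This rests on the protocol's 60 events in 300 patients, on counting the VA/civilian term as one variable, and on taking the events-per-variable rule as the protocol's chosen standard. It does not depend on that rule being the best way to size a penalised model.

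The consequence is limited to a higher risk of overfitting in all three models if the stated capacity is used. Neither certain overfitting nor a biased omics comparison is shown. The event counts behind the AUC precision and power statements do not rest on the number of features.

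**What to change.** In Aim 2.1 (Power calculations), do one of the following:

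1. Replace the claim of about 10 clinical features with 4 to 6 variables, including the VA/civilian term, based on the 60 events in the 300 model-building patients.
2. Drop the events-per-variable rule and justify a longer candidate list on another stated basis, such as LASSO penalisation.

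Under either option, name the 300 model-building patients as the basis, so that the overall sample size is not read as including the validation set.

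A cap on the clinical baseline model is optional. If one is considered, note that shortening the clinical list while leaving the omics list open could leave out real clinical predictors and so favour the omics models.

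The first option costs one restated figure, and the second a short paragraph of justification. Neither changes recruitment, assays, endpoints or timeline.
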